| Physical Examination (recorded in source document)   | X               | X                |                | X              | X              | X              |                | X                       | 
 
Day 1 complete physical exam pre-dose.
 
After Day 1, brief physical exam.
 
See Section 8.3.1.
 
See Appendix 10C in Section 10.10.3 for suggested chronology of assessments.
 
                                 |
| Body Weight  | X               |                  |                |                | X              |                | X              |                         | 
 
See Section 8.3.1.
 
  |
| Length / Head Circumference  | X               |                  |                |                |                |                |                |                         | 
 
See Section 8.3.1.
 
  |
| Vital signs including SpO 2   | X               | X                |                | X              | X              | X              |                | X                       | 
 
Before PK, NP swabs and IMP administration (See Appendix 10C in Section 10.10.3 for proposed chronology of assessment).
 
If hospitalized collect once daily until discharge and per SoA after discharge. See Section 8.3.2.
 
 |
| 12-Lead ECG  | X               |                  |                |                |                |                |                |                         | 
 
ECG may be performed after screening as needed per investigator discretion.
 
See Section 8.3.3 for ECG details.
 
See Appendix 10C in Section 10.10.3 for proposed chronology of assessment.
 
                         |
| Record Supplemental O 2 need  | X               | X                | X              | X              | X              | X              | X              | X                       | 
 
See Section 8.3.2.3.
 
  |

PFIZER CONFIDENTIAL

CT02-GSOP Clinical Protocol Template Phase 1 2 3 4 (14 April 2023)

Page 28

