|   |  | feed (up to 5.4 mL, based on 95 th percentile weight for a 2-year-old).  |
| Impact to participant with regard to study participation, including assessments and visits. | 
Clinical management of participant when there is worsening of RSV infection resulting in hospitalization.
 
Continuing in the study when participant is enrolled as an inpatient and is discharged later.
 
Study Day [REDACTED] or [REDACTED] requires an extended stay at the site (if the participant is outpatient at the time of visit) can be especially challenging.
 
Discomforts/concerns during study conduct for assessments including ECG, nasal swabs, blood draws and blood volumes.
 | 
Selection of sites with capabilities that allow for management of participants with changes from an outpatient to inpatient or inpatient to outpatient settings.
 
CCI [REDACTED] on Day [REDACTED] or [REDACTED] mitigate the challenges with an CCI [REDACTED] for participants in the outpatient setting.
 
For the 5-week duration of the study, the assessments, including blood draws and NP swabs, have been kept to a minimum for all cohorts where feasible.
 
There are currently no approved RSV antivirals and thus providing placebo does not lead to additional risks for the participant. The efficacy of sisunatovir is still being evaluated. All participants (placebo or sisunatovir) will continue to receive standard of care.
 |

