#### 4.2.3. Rationale for Comparator

There are currently no approved RSV antivirals available, and thus no active control can be proposed as comparator. The comparator for this study is participants receiving placebo. Each cohort evaluated in the study will have participants on placebo. The placebo group is required for assessing the safety, tolerability, and palatability of the study intervention.

All participants (including participants receiving placebo) enrolled in the study will receive the SOC. Participants enrolled in the study while in the outpatient setting may continue in the study if hospitalized at investigator discretion. C5241003 study that completed recruitment, was conducted to characterize the PK profile, safety and virologic response to sisunatovir in RSV-infected hospitalized children aged 1 month - 36 months and included an open-label Part A (1.0, 2.0 and 2.5 mg/kg single dose) and double-blind Part B (CCI [REDACTED]; 2.5 mg/kg, 3.5 mg/kg and 5 mg/kg q12h × 5 days). Initial pediatric dose recommendations for Cohort 1A, 1B, and 1C are based on observed concentrations in Study C5241003 with interpolation of predicted exposures, relative to exposure of CCI mg CCI in adults.

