## 7. DISCONTINUATION OF STUDY INTERVENTION AND PARTICIPANT DISCONTINUATION/WITHDRAWAL

### 7.1. Discontinuation of Study Intervention

It may be necessary for a participant to permanently discontinue study intervention. Reasons for permanent discontinuation of study intervention include the following:

- Death
- Occurrence of an AE or any other condition posing a risk to a participant or jeopardizing a safe continuation of the study treatment for the respective participant (as judged by the investigator, and/or the national coordinators, and/or the Medical Monitor and the study sponsor)
- Missing any dose prior to the [REDACTED] CCI draw

- Requirement of prohibited concomitant medications during the study (See [Appendix 8](#) in Section 10.8)
- Study terminated by sponsor

Discontinuation of study intervention does not represent withdrawal from the study. If study intervention is permanently discontinued, the participant should remain in the study to be evaluated for follow-up visits. Unplanned visits following permanent discontinuation of study intervention, if needed will be conducted per Day ~~CC1~~ visit in the [SoA](#). See the [SoA](#) for data to be collected at the time of discontinuation of study intervention and follow-up for any further evaluations that need to be completed.

In the event of discontinuation of study intervention, it must be documented on the appropriate CRF/in the medical records whether the participant is discontinuing further receipt of study intervention or also from study procedures, further study follow-up, and/or future collection of additional information.

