### 7.2. Participant Discontinuation/Withdrawal From the Study

A participant may withdraw from the study at any time at their own request, or at the request of the parent(s)/legal guardian. Reasons for discontinuation from the study include the following:

- Refused further study procedures;
- Lost to follow up;
- Death;
- Investigator decision;
- Study terminated by sponsor;

- Withdrawal of consent/assent by parent(s)/legal guardian or by a child who has provided assent during any phase of the study

At the time of discontinuing from the study, if possible, an early discontinuation visit should be conducted. See the [SoA](#) for assessments to be collected at the time of study discontinuation and follow-up and for any further evaluations that need to be completed.

The early discontinuation visit applies only to participants who are enrolled/randomized and then are prematurely withdrawn from the study. Participants/participant's parent(s)/legal guardian should be questioned regarding their reason for withdrawal.

The participant will be permanently discontinued from the study intervention and the study at that time.

If a participant/participant's parent(s)/legal guardian withdraws from the study, they may request destruction of any remaining samples taken and not tested, and the investigator must document any such requests in the site study records and notify the sponsor accordingly.

If the participant withdraws from the study and also withdraws assent (see Section 7.2.1) for disclosure of future information, no further evaluations will be performed, and no additional data will be collected. The sponsor may retain and continue to use any data collected before such withdrawal of assent.

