#### **8.4.1. Time Period and Frequency for Collecting AE and SAE Information**

The time period for actively eliciting and collecting AEs and SAEs ("active collection period") for each participant begins from the time the parent(s)/legal guardian provides informed consent, which is obtained before undergoing any study-related procedure and/or receiving study intervention, through and including a minimum of 28 calendar days, except as indicated below, after the last administration of the study intervention.

Follow-up by the investigator continues throughout the active collection period and until the AE or SAE or its sequelae resolve or stabilize at a level acceptable to the investigator.

When a clinically important AE remains ongoing at the end of the active collection period, follow-up by the investigator continues until the AE or SAE or its sequelae resolve or stabilize at a level acceptable to the investigator and Pfizer concurs with that assessment.

For participants who are screen failures, the active collection period ends when screen failure status is determined.

If the parent(s)/legal guardian withdraws the participant from the study and also withdraws consent for the collection of future information, the active collection period ends when consent is withdrawn.

If a parent(s)/legal guardian permanently discontinues or temporarily discontinues study intervention (because of an AE or SAE, the AE or SAE must be recorded on the CRF and the SAE reported using the CT SAE Report Form/ PSSA.

Investigators are not obligated to actively seek information on AEs or SAEs after the participant has concluded study participation. However, if the investigator learns of any SAE, including a death, at any time after a participant has concluded study participation, and they consider the event to be reasonably related to the study intervention, the investigator must promptly report the SAE to Pfizer via PSSA.

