6.6.8. Medically Attended Visit

The total number of all outpatient visits, the number of emergency room visits, and the number of urgent care visits for each patient will be summarized descriptively as described in Section 5.2.1 by treatment, cohort, and age band.

The number and percentage of participants who have been hospitalized post-randomization, will be summarized descriptively as described in Section 5.2.2 by treatment, cohort, and age band. The number and percentage of participants requiring inpatient stays and the number and percentage of participants with ICU stay will also be summarized descriptively as described in Section 5.2.2 by treatment, cohort, and age band.

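### Section 4.2.3 leaves it to the investigator whether an admitted outpatient stays in the study, which conflicts with the retention and AE-collection rules in 7.1, 7.2.1 and 8.4.1

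*Protocol*

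**What the plan says.** Protocol 4.2.3 (Rationale for Comparator) contains the only rule I found on whether a child enrolled as an outpatient stays in the trial after admission: "Participants enrolled in the study while in the outpatient setting may continue in the study if hospitalized at investigator discretion".

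Protocol 7.2 lists "Investigator decision" among the reasons for leaving the study, without criteria. It asks for an early discontinuation visit if one is possible, and then states: "The participant will be permanently discontinued from the study intervention and the study at that time".

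Other sections point towards keeping the child:

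- Protocol 7.1, on stopping study drug: "If study intervention is permanently discontinued, the participant should remain in the study to be evaluated for follow-up visits".
- Protocol 7.2.1: when parents ask to stop drug, follow-up is mandatory, and the sole exception is withdrawal of consent for further contact.
- Protocol 8.4.1: AEs and SAEs are actively collected for at least 28 days after the last dose. The early ends it lists are screen failure and withdrawal of consent for future information. It also says: "Investigators are not obligated to actively seek information on AEs or SAEs after the participant has concluded study participation".
- Protocol 2.3.1, as mitigation for worsening RSV that leads to admission: "Selection of sites with capabilities that allow for management of participants with changes from an outpatient to inpatient".
- Schedule of Activities, vital signs: "If hospitalized collect once daily until discharge and per SoA after discharge".

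SAP 6.6.8 summarizes, by treatment, cohort and age band: "The number and percentage of participants who have been hospitalized post-randomization". It does the same for ICU stays.

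**The concern.** The sentence in 4.2.3 attaches the discretion to the study and not to the study drug. Admission is a marker of worsening RSV and an outcome reported by treatment arm. If admission can lead to exit, the length of observation can depend on how the child is doing.

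The primary endpoints are incidences of adverse events, of discontinuations due to them, and of clinically significant laboratory and vital-sign abnormalities, set against placebo. SAP 3.1.1 counts treatment-emergent events from first dose until the end of the study. A child who leaves at admission has less time in which such events can be seen.

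Protocol 2.3.2 names prevention of hospitalization as a possible benefit. If the drug has that effect, more placebo children would be exposed to early exit and later harm on placebo could be understated. If the drug caused admissions, the reverse could occur. Several interruption rules in 4.1.1 are triggered by two events or two participants, so a single unobserved later event could matter.

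**Working it through.** No arithmetic applies: the plan states no figure on this point. The check is a side-by-side reading.

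1. **What is discretionary.** 4.2.3 refers to continuing in the study. It gives no criteria and does not separate dosing from follow-up.
2. **Is there a route out?** Yes. 7.2 accepts the investigator's decision as a reason and ends drug and study participation together. The early discontinuation visit is conditional on being possible.
3. **What happens to AE collection after exit?** 8.4.1 gives two answers. Its 28-day minimum lists no exception for removal by the investigator. Its later sentence releases the investigator from actively seeking events once participation has concluded. The section does not say which governs a child removed before the 28 days are over.
4. **How does this compare with stopping drug?** Under 7.1, a child who stops drug for any reason should remain for follow-up visits. Under 7.2.1, a child whose parents ask to stop drug must be followed unless consent for contact is withdrawn. A family's request to stop drug therefore brings mandatory follow-up, while an admission makes follow-up optional.
5. **Is inpatient status a design reason for exit?** No. Protocol 4.1 enrolls hospitalized as well as outpatient children, and exclusion criterion 10 keeps children on high-flow nasal cannula or CPAP eligible. The Schedule of Activities already provides daily vital signs and daily RSV signs and symptoms for inpatients.
6. **Is the child lost from the analysis?** No. The safety analysis set (Protocol 9.2, SAP 4) holds every randomized child who took at least one dose. What can be lost is later observation.
7. **What does the early discontinuation visit recover?** If it takes place, the Schedule of Activities marks vital signs, physical examination, RSV signs and symptoms, a nasopharyngeal swab, AE review and a PK sample. Its notes waive PK only after the treatment period and safety laboratory tests only after a given visit. This captures status at exit, not what happens afterwards.
8. **Does SAE follow-up close the gap?** Only in part. Events already reported are followed until they resolve or stabilize (8.4.1). Under Appendix 3, expected progression of the disease under study is not an AE unless more severe than expected, so an RSV admission is not automatically an SAE.
9. **Does the SAP table still count the admission?** It can, because the admission precedes the exit. A later ICU stay or a new event might not be recorded.
10. **Size.** The total is capped at 108, but the number per cell and the active-to-placebo split are redacted. Neither document gives an expected admission rate or removal rate.

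**The case against.** The best reply is that 4.2.3 grants a permission in a rationale section and orders no removal. Hospitalization appears in neither the 7.1 list of reasons for stopping drug nor the 7.2 list of reasons for leaving the study. The risk table treats admission as something sites are selected to manage, so the intent seems to be retention. The inpatient schedule would be needed anyway, because inpatients are enrolled, so it does not by itself contradict 4.2.3. Site staff are blinded and cannot knowingly favor an arm. There are no hypotheses, and all analyses are descriptive.

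Most of this stands. It shows that removal is permitted rather than required or expected. It does not settle the matter, because the one sentence that states a rule makes study participation optional, and a site could reasonably apply it. Blinding prevents deliberate selection by arm, but not unequal truncation if admissions themselves differ by arm. A descriptive comparison with placebo is still the primary objective.

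A reader might infer that 4.2.3 itself ends safety follow-up for children who deteriorate. The documents do not support that: the 28-day collection lists no exception for investigator removal, reported events are followed to resolution or stabilization, and an early discontinuation visit is called for if possible.

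**Conclusion.** The inconsistency is real. Read with 7.2 and the closing part of 8.4.1, 4.2.3 permits exit that depends on clinical worsening, contrary to the retention rules in 7.1 and 7.2.1 and to the 28-day collection in 8.4.1. The consequence is possible shorter observation of the primary safety endpoints in children who do badly. They are not excluded from the safety set.

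The size cannot be computed. A reader might try 108 divided by 12 cohort-by-age cells, which is 9 per cell, assume a 6:3 split, and conclude that one removed child is 1/6 = 17% of the active or 1/3 = 33% of the placebo children in that cell. The split is an assumption, 108 is the maximum including repeat-dose enrollment, and the removed child stays in the denominator. A reader might also take an exit and last dose on Day 3, so that collection should run to Day 31, and conclude that 28/31 = 90% of the period is lost. That requires the 28-day duty to end at removal, which 8.4.1 does not list.

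The conclusion rests on the wording alone and assumes nothing about how often investigators would use the discretion.

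**What to change.** Reconcile 4.2.3 and 7.2 with 7.1, 7.2.1 and 8.4.1. State that participants hospitalized after enrollment remain in the study for the scheduled safety follow-up and the 28-day AE and SAE collection unless consent is withdrawn. In 7.2, state that hospitalization alone is not a ground for study discontinuation by the investigator's decision.

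This concerns retention and data collection only. Whether study drug continues is left to the existing discontinuation provisions, and no view is taken on it.

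The cost is a sentence in 4.2.3 and a clause in 7.2, plus some added follow-up work for admitted children. Inpatient assessments and sites able to manage a change of setting are already part of the plan.

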#### 4.3. Justification for Dose

The current study will evaluate safety, tolerability, PK, and guidance for future dosing of sisunatovir in a broader pediatric population (1 day to 60 months of age) with RSV-LRTI for further clinical development of sisunatovir.

To investigate the effect of sisunatovir on clinical activity following RSV infection, a viral challenge clinical study in healthy adult participants was conducted where doses of 200 mg or 350 mg Q12 × 5 days were administered following inoculation of an RSV infection (C5241002). In this study, at both doses evaluated, sisunatovir robustly decreased viral load and alleviated RSV symptoms relative to placebo. While statistically significant differences were not observed between the two dose levels relative to placebo, the 350 mg dose effect was numerically larger than the 200 mg dose. Pediatric doses are expected to produce systemic steady-state exposures comparable to the adult dose of 200 mg q12h that was found to be effective in treating viral load and symptoms of RSV in the challenge study.

Additionally, sisunatovir was administered in a completed ex-US Phase 2 study (C5241003, previously REVC003) to characterize the PK profile, safety and virologic response to sisunatovir in RSV-infected hospitalized children aged 1 month -36 months. Participants 1 month to <6 months of age were administered sisunatovir up to 2.5 mg/kg q12h for 5 days. Participants 6 months to 36 months of age were administered sisunatovir up to 5.0 mg/kg q12h for 5 days. The highest dose in each age group provided mean exposures above EC90 and below the pre-specified upper exposure limit of 294 ng/mL. Overall, sisunatovir was found to be safe for infants and children ≥1 month to ≤36 months. These results support the current study to establish safety, tolerability, PK, and guidance for dosing of sisunatovir in a broader pediatric population (1 day up to 60 months) with RSV-LRTI for further clinical development of sisunatovir.

Initial pediatric dose recommendations for Cohort 1A, 1B, and 1C are based on observed concentrations in Study C5241003 with interpolation of predicted exposures, relative to

exposure of **CCI** mg **CCI** in adults. The proposed starting dose of sisunatovir for participants **CCI** is **CCI** mg/kg and for participants **CCI** is **CCI** mg/kg (see Table 4). These doses are **CCI** than those administered in **CCI**, which were well below the PK stopping limit NOAELs.

**Table 4. Cohort 1 Dose Recommendations**

|                | CCI
CCI | CCI (preliminary) GeoMean (%CV) |                         |                         | CCI
CCI |
|----------------|--------------------------|--|-------------------------|-------------------------|--------------------------|
|                | CCI
(n=11)     | 3.5 mg/kg
(n=3)                     | Predicted
CCI | Predicted
CCI | 5 mg/kg
(n=2)         |
| $C_{troughSS}$ | 42 (190)                 | 17 (200)                               |                         |                         | 69 (30)                  |
| $C_{maxSS}$    | 111 (146)                | 36 (249)                               |                         |                         | 181 (98)                 |
| $AUC_{SS}$     | 869 (121)                | 264 (224)                              |                         |                         | 1380 (79)                |

Based on analysis of PK and safety data from Cohort 1, the doses for Cohort 2 may be adjusted to more closely match the **CCI** mg dose in **CCI** or to gather additional data on doses used in Cohort 1. To support this, an iterative population PK model is being developed to support further pediatric dose recommendations. This model is developed with successive updates and validations from all available adult and pediatric data as studies complete, including Part A and B of C5241003. It is anticipated that the weight-based dose will be adjusted for pediatric patients by age, based on maturation of **CCI** liver function. The **CCI** dose of sisunatovir for **CCI** will be determined after evaluation of **CCI**. The specific dose and **CCI** in optional Cohort 3 will be determined upon review of Cohorts 1 and/or 2 but will not exceed exposures found to be well tolerated in adults (C5241006). Sponsor will determine which age groups in Cohort 3 need additional exposure, safety or tolerability data for a given dose.

